**Table 2. Protocol-Required Safety Laboratory Assessments**

Hematology	Chemistry	Urinalysis	Other
Hemoglobin	BUN/urea and creatinine	pH	At screening only:
Hematocrit	Glucose (fasting)	Glucose (qual)	• FSH b
RBC count	Calcium	Protein (qual)	• Urine drug screening c
MCV	Sodium	Blood (qual)	• Hepatitis B surface antigen
MCH	Potassium	Ketones	• Hepatitis B core antibody
MCHC	Chloride	Nitrites	• Hepatitis C antibody
Platelet count	AST, ALT	Leukocyte esterase	• Human immunodeficiency virus
PT/INR	Total bilirubin	Urobilinogen	
WBC count	Alkaline phosphatase	Urine bilirubin	
Total neutrophils (abs)	Albumin	Microscopy a	
Eosinophils (abs)	Total protein		
Monocytes (abs)			
Basophils (abs)			
Lymphocytes (abs)			

Abbreviations: abs = absolute; ALT = alanine aminotransferase; AST = aspartate aminotransferase; BUN = blood urea nitrogen; FSH = follicle-stimulating hormone; INR = international normalized ratio; MCH = mean corpuscular hemoglobin; MCHC = mean corpuscular hemoglobin concentration; MCV = mean corpuscular volume; qual = qualitative; PT = prothrombin time; RBC = red blood cell; WBC = white blood cell.

- Only if urine dipstick is positive for blood, protein, nitrites, or leukocyte esterase.
- For confirmation of postmenopausal status only.
- The minimum requirement for drug screening includes cocaine, tetrahydrocannabinol (THC), opiates/opioids, benzodiazepines, and amphetamines (others are site and study specific).

Investigators must document their review of each laboratory safety report.

Any remaining serum/plasma from samples collected for clinical safety laboratory measurements at baseline and at all times after dose administration may be retained and stored for the duration of the study. Upon completion of the study, these retained safety samples may be used for the assessment of exploratory safety biomarkers or unexpected safety findings. These data will not be included in the clinical study report (CSR). Samples to be used for this purpose will be shipped to either a Pfizer-approved Biospecimen Banking System (BBS) facility or other designated laboratory and retained for up to 1 year following the completion of the study.

### **10.3. Appendix 3: Adverse Events: Definitions and Procedures for Recording, Evaluating, Follow-up, and Reporting**

#### **10.3.1. Definition of AE**

AE Definition

• An AE is any untoward medical occurrence in a patient or clinical study participant, temporally associated with the use of study intervention, whether or not considered related to the study intervention.

• NOTE: An AE can therefore be any unfavorable and unintended sign (including an abnormal laboratory finding), symptom, or disease (new or exacerbated) temporally associated with the use of study intervention.

Events Meeting the AE Definition

• Any abnormal laboratory test results (hematology, clinical chemistry, or urinalysis) or other safety assessments (eg, ECG, radiological scans, vital sign measurements), including those that worsen from baseline, considered clinically significant in the medical and scientific judgment of the investigator (ie, not related to progression of underlying disease).

• Exacerbation of a chronic or intermittent preexisting condition including either an increase in frequency and/or intensity of the condition.

• New conditions detected or diagnosed after study intervention administration even though it may have been present before the start of the study.

• Signs, symptoms, or the clinical sequelae of a suspected drug-drug interaction.

• Signs, symptoms, or the clinical sequelae of a suspected overdose of either study intervention or a concomitant medication. Overdose per se will not be reported as an AE/SAE unless it is an intentional overdose taken with possible suicidal/self-harming intent. Such overdoses should be reported regardless of sequelae.

Events NOT Meeting the AE Definition


• Any clinically significant abnormal laboratory findings or other abnormal safety assessments which are associated with the underlying disease, unless judged by the investigator to be more severe than expected for the participant's condition.

• The disease/disorder being studied or expected progression, signs, or symptoms of the disease/disorder being studied, unless more severe than expected for the participant's condition.

• Medical or surgical procedure (eg, endoscopy, appendectomy): the condition that leads to the procedure is the AE.

• Situations in which an untoward medical occurrence did not occur (social and/or convenience admission to a hospital).

• Anticipated day-to-day fluctuations of preexisting disease(s) or condition(s) present or detected at the start of the study that do not worsen.

### 10.3.2. Definition of SAE

If an event is not an AE per definition above, then it cannot be an SAE even if serious conditions are met (eg, hospitalization for signs/symptoms of the disease under study, death due to progression of disease).

An SAE is defined as any untoward medical occurrence that, at any dose:
a. Results in death
b. Is life-threatening The term "life-threatening" in the definition of "serious" refers to an event in which the participant was at risk of death at the time of the event. It does not refer to an event that hypothetically might have caused death if it were more severe.
c. Requires inpatient hospitalization or prolongation of existing hospitalization In general, hospitalization signifies that the participant has been detained (usually involving at least an overnight stay) at the hospital or emergency ward for observation and/or treatment that would not have been appropriate in the physician's office or outpatient setting. Complications that occur during hospitalization are AEs. If a complication prolongs hospitalization or fulfills any other serious criteria, the event is serious. When in doubt as to whether "hospitalization" occurred or was necessary, the AE should be considered serious. Hospitalization for elective treatment of a preexisting condition that did not worsen from baseline is not considered an AE.
d. Results in persistent disability/incapacity 

• The term disability means a substantial disruption of a person's ability to conduct

normal life functions.
 
 
This definition is not intended to include experiences of relatively minor medical significance such as uncomplicated headache, nausea, vomiting, diarrhea, influenza, and accidental trauma (eg, sprained ankle) which may interfere with or prevent everyday life functions but do not constitute a substantial disruption.
 

e. Is a congenital anomaly/birth defect
f. Other situations: 
 
Medical or scientific judgment should be exercised in deciding whether SAE reporting is appropriate in other situations such as important medical events that may not be immediately life-threatening or result in death or hospitalization but may jeopardize the participant or may require medical or surgical intervention to prevent one of the other outcomes listed in the above definition. These events should usually be considered serious.
 
Examples of such events include invasive or malignant cancers, intensive treatment in an emergency room or at home for allergic bronchospasm, blood dyscrasias or convulsions that do not result in hospitalization, or development of drug dependency or drug abuse.
 

### 10.3.3. Recording/Reporting and Follow-up of AEs and/or SAEs

AE and SAE Recording/Reporting		

The table below summarizes the requirements for recording adverse events on the CRF and for reporting serious adverse events on the Clinical Trial (CT) Serious Adverse Event (SAE) Report Form to Pfizer Safety. These requirements are delineated for 3 types of events: (1) SAEs; (2) nonserious adverse events (AEs); and (3) exposure to the IP under study during pregnancy or breastfeeding, and occupational exposure.
 
It should be noted that the CT SAE Report Form for reporting of SAE information is not the same as the AE page of the CRF. When the same data are collected, the forms must be completed in a consistent manner. AEs should be recorded using concise medical terminology and the same AE term should be used on both the CRF and the CT SAE Report Form for reporting of SAE information.
		
Safety Event	Recorded on the CRF	Reported on the CT SAE Report Form to Pfizer Safety Within 24 Hours of Awareness
SAE	All	All
Nonserious AE	All	None

Exposure to the investigational product under study during pregnancy or breastfeeding, and occupational exposure
	
None
	
All (and exposure during pregnancy [EDP] supplemental form for EDP)

 
• When an AE/SAE occurs, it is the responsibility of the investigator to review all documentation (eg, hospital progress notes, laboratory reports, and diagnostic reports) related to the event.
 
• The investigator will then record all relevant AE/SAE information in the CRF.
 
• It is not acceptable for the investigator to send photocopies of the participant’s medical records to Pfizer Safety in lieu of completion of the CT SAE Report Form/AE/SAE CRF page.
 
• There may be instances when copies of medical records for certain cases are requested by Pfizer Safety. In this case, all participant identifiers, with the exception of the participant number, will be redacted on the copies of the medical records before submission to Pfizer Safety.
 
• The investigator will attempt to establish a diagnosis of the event based on signs, symptoms, and/or other clinical information. Whenever possible, the diagnosis (not the individual signs/symptoms) will be documented as the AE/SAE.
 
		

Assessment of Intensity
		

The investigator will make an assessment of intensity for each AE and SAE reported during the study and assign it to 1 of the following categories:
 
 
• Mild: An event that is easily tolerated by the participant, causing minimal discomfort and not interfering with everyday activities.
 
• Moderate: An event that causes sufficient discomfort and interferes with normal everyday activities.
 
• Severe: An event that prevents normal everyday activities. An AE that is assessed as severe should not be confused with an SAE. Severe is a category utilized for rating the intensity of an event; and both AEs and SAEs can be assessed as severe.
 
 
An event is defined as “serious” when it meets at least 1 of the predefined outcomes as described in the definition of an SAE, NOT when it is rated as severe.
		

#### Assessment of Causality

- The investigator is obligated to assess the relationship between study intervention and each occurrence of each AE/SAE.
- A “reasonable possibility” of a relationship conveys that there are facts, evidence, and/or arguments to suggest a causal relationship, rather than a relationship cannot be ruled out.
- The investigator will use clinical judgment to determine the relationship.
- Alternative causes, such as underlying disease(s), concomitant therapy, and other risk factors, as well as the temporal relationship of the event to study intervention administration will be considered and investigated.
- The investigator will also consult the investigator’s brochure (IB) and/or product information, for marketed products, in his/her assessment.
- For each AE/SAE, the investigator must document in the medical notes that he/she has reviewed the AE/SAE and has provided an assessment of causality.
- There may be situations in which an SAE has occurred and the investigator has minimal information to include in the initial report to the Sponsor. However, it is very important that the investigator always make an assessment of causality for every event before the initial transmission of the SAE data to the Sponsor.
- The investigator may change his/her opinion of causality in light of follow-up information and send an SAE follow-up report with the updated causality assessment.
- The causality assessment is one of the criteria used when determining regulatory reporting requirements.
- If the investigator does not know whether or not the IP caused the event, then the event will be handled as “related to IP” for reporting purposes, as defined by the Sponsor. In addition, if the investigator determines that an SAE is associated with study procedures, the investigator must record this causal relationship in the source documents and CRF, and report such an assessment in the dedicated section of the CT SAE Report Form and in accordance with the SAE reporting requirements.

**Follow-up of AEs and SAEs**

- The investigator is obligated to perform or arrange for the conduct of supplemental measurements and/or evaluations as medically indicated or as requested by the Sponsor to elucidate the nature and/or causality of the AE or SAE as fully as possible. This may include additional laboratory tests or investigations, histopathological examinations, or consultation with other healthcare professionals.
- If a participant dies during participation in the study or during a recognized follow-up period, the investigator will provide Pfizer Safety with a copy of any postmortem findings including histopathology.
- New or updated information will be recorded in the originally completed CRF.
- The investigator will submit any updated SAE data to the Sponsor within 24 hours of receipt of the information.

**10.3.4. Reporting of SAEs**

**SAE Reporting to Pfizer Safety via an Electronic Data Collection Tool**

- The primary mechanism for reporting an SAE to Pfizer Safety will be the electronic data collection tool.
- If the electronic system is unavailable, then the site will use the paper SAE data collection tool (see next section) in order to report the event within 24 hours.
- The site will enter the SAE data into the electronic system as soon as the data become available.
- After the study is completed at a given site, the electronic data collection tool will be taken off-line to prevent the entry of new data or changes to existing data.
- If a site receives a report of a new SAE from a study participant or receives updated data on a previously reported SAE after the electronic data collection tool has been taken off-line, then the site can report this information on a paper SAE form (see next section) or to Pfizer Safety by telephone.

**SAE Reporting to Pfizer Safety via CT SAE Report Form**

- Facsimile transmission of the CT SAE Report Form is the preferred method to transmit this information to Pfizer Safety.
- In circumstances when the facsimile is not working, notification by telephone is acceptable with a copy of the CT SAE Report Form sent by overnight mail or courier service.
- Initial notification via telephone does not replace the need for the investigator to complete and sign the CT SAE Report Form pages within the designated reporting time frames.

## **10.4. Appendix 4: Contraceptive Guidance and Collection of Pregnancy Information**

### **10.4.1. Male Participant Reproductive Inclusion Criteria**

Male participants are eligible to participate if they agree to the following requirements during the intervention period and for at least 3 weeks after the last dose of study intervention, which corresponds to the time needed to eliminate study intervention(s) (eg, 5 terminal half-lives) plus an additional 90 days (a spermatogenesis cycle):

- Refrain from donating sperm.

PLUS either:

- Be abstinent from heterosexual or homosexual intercourse as their preferred and usual lifestyle (abstinent on a long-term and persistent basis) and agree to remain abstinent;

OR

- Must agree to use contraception/barrier as detailed below:
  - Agree to use a male condom when engaging in any activity that allows for passage of ejaculate to another person.
  - Use of an additional highly effective contraceptive method with a failure rate of <1% per year as described below in [Section 10.4.4](#) for a female partner of childbearing potential.

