- g. Safety laboratory assessments including urinalysis, hematology (including prothrombin time/partial thromboplastin time), and chemistry will be performed at Screening, on Day -1, on Day 2, Day 7 prior to discharge and during early termination. All assessments must be collected following at least a 4-hour fast. For participants with severe hepatic impairment (Cohort 1), the Day -1 safety labs including liver function assessments and evaluation of renal function must be completed prior to dacomitinib dosing on Day 1, for review of inclusion/exclusion criteria. Additional assessments may be performed at the discretion of the investigator.
- h. On Day -1, on Day 7 (or any subsequent day that coincides with discharge) and during follow-up or early termination, the investigator or his/her designee will discuss with the participant the need to use highly effective contraception consistently and correctly according to protocol contraception guidelines in [Section 5.3.4](#).
- i. Alcohol/tobacco use and alcohol breath test will be performed during Screening or on Day -1. These tests may also be performed at any other time at the discretion of the investigator.
- j. A single 12-lead ECG will be obtained at Screening, 6 hours post-dose on Day 1, prior to discharge on Day 7 and during early termination. A triplicate ECG will be obtained approximately 2 to 4 minutes apart at pre-dose on Day 1. All ECG assessments will be made following at least a 10-minute rest in a supine position and should be collected before PK sample collection, if scheduled at the same time point.
- k. Supine blood pressure will be determined following approximately 5-minute rest in a supine position.
- l. The modified Child-Pugh assessment as outlined in [Appendix 8](#) should be followed.
- m. On Day 1, administration of dacomitinib will occur with approximately 8 oz (240 mL) of ambient temperature water after at least a 10 hour fast. Following dacomitinib administration, no food will be allowed for at least another 4 hours post dose except that a light snack or juice may be provided to a diabetic participant.
- n. Blood samples (3 mL each) for PK will be taken upon completion of ECGs, blood pressure and pulse measurements. Serial blood samples for the measurements of dacomitinib and its metabolite, PF-05199265, will be collected prior to dosing and at 2, 4, 6, 8, 12, 24, 48, 72, 96, 120, 144, 168, 192, 216 and 264 hours following dosing.

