- o. Blood samples (10 mL each) will be collected prior to dacomitinib dosing and at 6 and 8 hours following dosing.
- p. One (1) blood sample (3 mL) only will be collected on Day -1 for CYP2D6 genotyping.
- q. One (1) 4 mL blood sample should be drawn on Day -1. If not collected on the designated collection day, collect at the next available time point when biospecimens are being collected in conjunction with a participant visit.
- r. Participants will be eligible for discharge from the CRU following completion of the following: 144-hour PK sample collection, a single supine 12-lead ECG, supine blood pressure and pulse rate, discussion of the need for highly effective contraception, safety laboratory test, evaluation of participant-reported adverse events, review of prior and concomitant medications, brief physical examination, and body weight. Day 7 safety laboratory tests can be collected early (ie. On Day 6) so results are available in time for intended participant discharge on that day.
- s. All participants will be followed up by phone call at least 28 days and up to 35 days after the administration of the dacomitinib dose for potential AEs, concomitant treatment use and to confirm appropriate contraception usage.
- t. Participant withdrawal/early termination activities will include a brief physical examination (if there is a new or ongoing AE or a previous clinically significant abnormal physical finding), safety laboratory tests, a contraception check, a single supine 12-lead ECG, supine blood pressure and pulse rate, concomitant treatment and AE assessment.

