#### 2.2.4. Clinical Overview

As of 29 July 2016, 3182 patients have been treated in 17 clinical studies and 143 healthy participants and 15 patients with solid tumors have been treated in 9 clinical pharmacology studies. Dacomitinib was administered to 2148 of the patients in these trials, in 1975 patients as a single agent or in combination with figitumumab (CP-751,871, a monoclonal antibody targeting the IGF1R), crizotinib (an anaplastic lymphoma kinase [ALK], mesenchymal-epithelial transition [MET] and c-ROS oncogene 1 [ROS1] tyrosine kinase inhibitor), or gedatolisib (PF-05212384, a phosphoinositide 3-kinase [PI3K]/mTOR inhibitor), and in 173 patients in Phase 1 combination therapy studies. Most patients treated in clinical studies had locally advanced or metastatic NSCLC. There were 1473 patients with NSCLC who received single-agent dacomitinib 45 mg once daily (QD), the maximum tolerated dose as determined by Studies A7471001, A7471003, and A7471005. Of these patients, 394 patients had NSCLC with EGFR-activating mutations; 255 of these patients received dacomitinib as first-line treatment.

The most frequently reported adverse events (AEs) in  $\geq 10\%$  of patients included GI-related, skin-and-nail-related, respiratory, and constitutional events.

Results from Study A7471015 indicated that dacomitinib can be administered with or without food. Following a single oral administration of dacomitinib at 45 mg in patients with advanced malignant solid tumors, the median time to reach the maximum observed plasma concentration ( $T_{max}$ ) of dacomitinib occurred approximately at 5 to 6 hours after dosing. Dacomitinib underwent extensive extravascular distribution with a geometric mean apparent volume of distribution ( $V_z/F$ ) ranging from 2424 to 2537 L/h and had a mean apparent terminal plasma half-life ( $t_{1/2}$ ) ranging from 54 to 80 hours. Following administration of multiple daily doses of dacomitinib at 45 mg to patients with advanced malignant solid tumors, steady-state was reached within 14 days, accumulation of dacomitinib in patients ranged from 5.0 to 6.4-fold for AUC, reflecting the observed long  $t_{1/2}$ . The geometric AUC over dosing interval ( $AUC_{tau}$ ) and  $C_{max}$  of dacomitinib at steady-state ranged from 1621 to 2213 ng•h/mL and 79.5 to 108.0 ng/mL, respectively. Plasma exposure of dacomitinib increased proportionally with dose in the dose range of 2 mg to 60 mg, indicating linear PK.

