#### 5.1.1. All Participants

##### Age and Sex:

1. Male and/or female participants of non-childbearing potential must be 18 to 75 years of age, inclusive, at the time of signing the informed consent document (ICD).
  - Refer to [Appendix 4](#) for reproductive criteria for male ([Section 10.4.1](#)) and female ([Section 10.4.2](#)) participants.

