##### **8.3.5.1. Exposure During Pregnancy**

Details of all pregnancies in female partners of male participants will be collected after the start of study intervention and until 3 weeks after the last dose.

If a pregnancy is reported, the investigator should inform the Sponsor within 24 hours of learning of the pregnancy and should follow the procedures outlined in [Appendix 4](#).

Abnormal pregnancy outcomes (eg, spontaneous abortion, fetal death, stillbirth, congenital anomalies, ectopic pregnancy) are considered SAEs.

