#### **8.4. Treatment of Overdose**

For this study, any dose of dacomitinib greater than 30 mg will be considered an overdose.

The Sponsor does not recommend specific treatment for an overdose.

In the event of an overdose, the investigator/treating physician should:

1. Contact the medical monitor immediately.
2. Closely monitor the participant for any AEs/SAEs and laboratory abnormalities until dacomitinib can no longer be detected systemically (at least 17 days,  $5 \times$  dacomitinib half-life).
3. Obtain a blood sample for PK analysis within 1 day from the date of the last dose of study intervention if requested by the medical monitor (determined on a case-by-case basis).
4. Document the quantity of the excess dose as well as the duration of the overdose in the CRF.
5. Overdose is reportable to Safety only when associated with an SAE.

Decisions regarding dose interruptions or modifications will be made by the investigator in consultation with the medical monitor based on the clinical evaluation of the participant.

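### The male contraception rule can be read as 21 or 111 days: 21 days does not match its stated basis, and 111 days outlasts partner-pregnancy collection by 90 days with no reason given

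*Protocol*

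**What the plan says.** Protocol Section 10.4.1 sets the period during which male participants must refrain from donating sperm and must be abstinent or use contraception. It covers the time on treatment and then lasts "at least 3 weeks after the last dose of study intervention, which corresponds to the time needed to eliminate study intervention(s"), with five terminal half-lives given as the example, "plus an additional 90 days (a spermatogenesis cycle"). Inclusion criterion 1 in Section 5.1.1 sends the reader to Appendix 4 "for reproductive criteria for male" participants, so the rule is a condition of eligibility.

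Other parts of the protocol bear on its length:

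- Section 2.2.4 gives a mean terminal half-life "ranging from 54 to 80 hours".
- Section 8.4 (overdose) asks for monitoring until dacomitinib "can no longer be detected systemically (at least 17 days", and equates this with five half-lives.
- Section 8.3.5.1 collects pregnancies in female partners "after the start of study intervention and until 3 weeks after the last dose".
- Schedule of Activities footnote h states that "during follow-up or early termination, the investigator or his/her designee will discuss with the participant the need to use highly effective contraception". Footnote s gives the timing of that contact: "All participants will be followed up by phone call at least 28 days and up to 35 days after the administration" of the dose.
- Section 5.3.4 (Contraception) gives no duration.

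**The concern.** The sentence in Section 10.4.1 supports two windows. On one reading, 3 weeks is the whole window, and the elimination time and the 90 days together are its justification. On the other, 3 weeks covers elimination only and the 90 days come on top. Each reading leaves a different problem. The first gives a window that its own basis does not support. The second gives a window that runs well past the end of partner-pregnancy collection, without explanation.

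What is at stake is consistent application of an eligibility and safety rule. Two sites could counsel men to durations that differ about five-fold, and each could believe it complies. If the longer window is meant, partner pregnancies are not actively collected for most of it.

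**Working it through.** **Inputs, all from the protocol.** Half-life 54 to 80 hours (2.2.4); five half-lives taken as at least 17 days (8.4); 3 weeks = 21 days and a further 90 days (10.4.1); partner-pregnancy collection to 21 days (8.3.5.1); follow-up call at days 28 to 35 (Schedule of Activities, footnote s).

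**Step 1. Try to reproduce 21 days from its stated basis** (five half-lives plus 90 days).

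- Half-life 54 h: 5 × 54 / 24 = 11.25 days; 11.25 + 90 = 101.25 days.
- Half-life 80 h: 5 × 80 / 24 = 16.7 days; 16.7 + 90 = 106.7 days.
- Section 8.4 figure: 17 + 90 = 107 days.

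The basis totals 101 to 107 days, so 21 days is not reproduced. The shortfall is 101.25 − 21 = 80 days to 107 − 21 = 86 days.

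**Step 2. Check 3 weeks against elimination alone.** 21 days exceeds 11.25 to 17 days, with about 4 to 10 days to spare. It would equal five half-lives at 21 × 24 / 5 = 100.8 hours. Three weeks therefore works as an elimination period, and reading it that way is plausible.

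**Step 3. Add the 90 days to the 3 weeks.** 21 + 90 = 111 days, and 111 / 21 = 5.3. Partner-pregnancy collection then ends 111 − 21 = 90 days before the window does.

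**Step 4. See whether the follow-up call settles it.**

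| Window | Call at days 28 to 35, relative to the end of the window |
|---|---|
| 21 days | 28 − 21 = 7 to 35 − 21 = 14 days after |
| 111 days | 111 − 35 = 76 to 111 − 28 = 83 days before |

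Discussing a need for contraception at days 28 to 35 fits poorly with a window that closed on day 21. The same call conflicts with nothing in a 111-day window, but it does not establish that window either.

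**Step 5. Look for a tie-breaker elsewhere.** Section 10.4.4 repeats that the spermatogenesis cycle is about 90 days, so the 90-day figure is not an isolated slip. Section 8.3.5.1 uses the same 3 weeks, which points the other way. No section states the total.

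**The case against.** The strongest reply is that the sentence means 3 weeks plus 90 days. The word additional suggests a sum, 3 weeks covers five half-lives on the protocol's figures, and Section 4.2 allows that half-life may be longer in severe impairment. The 21-day reading needs 3 weeks to correspond to a total that itself contains 90 days, so the five-fold contrast sets a coherent reading against an incoherent one. The 21 days is also worded as a minimum. On this view the fault is mainly one of punctuation.

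Much of that stands. The 111-day reading is self-consistent. But the only duration stated outright is 3 weeks, Section 8.3.5.1 uses the same figure, and the 111-day reading still leaves the 90-day mismatch with that section.

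Further points deserve credit:

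- Section 8.3.5.1 sets a collection period and not a contraception window. The mismatch is unexplained and is not a strict contradiction.
- Later partner pregnancies may still be reported. Section 5.3.4 has participants told to call at once about a known or suspected pregnancy in a partner, with no time limit. Section 8.3.5 makes exposure reportable on awareness. Appendix 4 defines paternal exposure without an end date. This cover is not complete, because Appendix 4 words one reporting duty as applying during treatment, which is unclear for a single dose.
- Footnote s describes the call as confirming appropriate contraception use, which could look back over a completed window. The call is therefore weak evidence either way.
- The half-life range comes from patients with advanced solid tumors, so 101 to 107 days is not firm for severe hepatic impairment. A longer half-life would only widen the gap to 21 days.
- The two problems are alternatives, one for each reading, and should not be added together.

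**Conclusion.** The point holds. Section 10.4.1 yields either a 21-day window that falls 80 to 86 days short of its stated basis, or a 111-day window that outlasts partner-pregnancy collection by 90 days without a reason. The two differ 5.3-fold, and nothing else in the protocol settles which is meant.

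The figures rest on the protocol's own half-life of 54 to 80 hours, its 17 days for five half-lives, and 3 weeks read as 21 days. If 111 days is intended, the gap is limited to active collection after week 3. The pharmacokinetic endpoints and their analysis are unaffected. The consent document was not available for this review, so whether it already states one duration is unknown. The text should be corrected because the rule governs eligibility, and Section 5 permits no waivers of enrollment criteria.

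**What to change.** - Reword the sentence in Section 10.4.1 so that it gives one total duration and a basis that adds up to it.
- Align the partner-pregnancy collection period in Section 8.3.5.1 with that duration, or state why it is shorter.
- Check that Schedule of Activities footnotes h and s, and the consent document, agree with the chosen duration.

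This review does not say which duration is right; that choice is the sponsor's. The cost is one reworded sentence in Section 10.4.1 and, depending on the intended duration, small edits to Section 8.3.5.1 or footnotes h and s, plus a check of the consent document.
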